## Study Summary Flow Diagram

#### 4.9. Primary Outcomes

- Time interval from Foley balloon placement to reaching the active phase of labor (6 cm cervical dilation)

#### 4.10 Secondary Outcomes

- Induction to delivery time in minutes
- Time interval from completion of cervical ripening to delivery in minutes
- Vaginal delivery within 24, 36 and 48 hours of induction
- Cesarean section rates and indications
- Operative delivery rates
- Total length of hospital stay
- Maternal outcomes
  - Isolated maternal fever
  - Chorioamnionitis (also known as “IAI,” or “triple I”):
    - A **presumptive diagnosis** of IAI (suspected triple I) can be made in women with:
      - **Fever** –  $\geq 39.0^{\circ}\text{C}$  [ $102.2^{\circ}\text{F}$ ] **or**  $38.0^{\circ}\text{C}$  [ $100.4^{\circ}\text{F}$ ] to  $38.9^{\circ}\text{C}$  [ $102.02^{\circ}\text{F}$ ] on two occasions 30 minutes apart, without another clear source **PLUS** one or more of the following [1]:
        - Baseline fetal heart rate  $>160$  beats/min for  $\geq 10$  minutes, excluding accelerations, decelerations, and periods of marked variability
        - Maternal white cell count  $>15,000/\text{mm}^3$  in the absence of corticosteroids and ideally showing a left shift (bandemia)
        - Purulent-appearing fluid coming from the cervical os visualized by speculum examination
      - A **confirmed diagnosis** of IAI can be made in women with:
        - **All of the above** **PLUS** one or more of the following objective laboratory findings:
          - Positive Gram stain of amniotic fluid
          - Low glucose level in amniotic fluid
          - Positive amniotic fluid culture
          - High white cell (WBC) count in amniotic fluid in the absence of a bloody tap
          - Histopathologic evidence of infection or inflammation or both in the placenta, fetal membranes, or the umbilical cord vessels (funisitis)
        - Endometritis - must meet the following criteria:
          - Infection occurs within 30 days after the operative procedure AND
          - Infection presumed to involve the uterus AND
          - Subject has at least one of the following:

- Purulent drainage from a drain that is placed through a stab wound into the abdomen or pelvis
- Organisms isolated from an aseptically-obtained culture of fluid or tissue in the organ / space
- Postpartum hemorrhage
  - EBL >1000 cc
- Wound infection
- Umbilical cord prolapse
- Neonatal outcomes
  - Apgar score <7 at 1 and 5 minutes
  - Cord arterial pH <7.0
  - NICU admission
  - Neonatal infection, defined as sepsis, fever, positive cultures, or a suspicious clinical course that warranted treatment with antibiotics

**5. Sub-Study Procedures:** No sub-studies will be performed

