**1. Introduction and Purpose:**

Amniotomy is a common practice in the management of labor induction. It is performed using a plastic hooked device to rupture the amniotic membranes. Currently at UTMB, it is left to the discretion of the provider to determine when amniotomy is performed during labor. There is little data to guide the timing of amniotomy. A recent meta-analysis suggests that amniotomy performed earlier in the labor course is associated with a decreased time from induction to delivery, with no change in rates of cesarean section. However, one study showed longer labors with an increase in rates of cesarean section with early amniotomy. Additionally, this meta-analysis was limited by the small number of trials included with varying methods of cervical ripening used prior to amniotomy, including Foley balloon, prostaglandins, or a combination. Lastly, in two of the studies included, spontaneous rupture of membranes was used as the control group, which does not provide clear guidance regarding the timing of amniotomy during labor, as in many cases amniotomy was not performed. Further data is needed to sufficiently evaluate the timing of amniotomy during induction, controlling for the method of cervical ripening.

The purpose of this study is to evaluate the impact of early versus delayed amniotomy on time from induction to the active phase of labor, as well on total time to delivery and maternal and neonatal outcomes in women undergoing cervical ripening with the Foley balloon.

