**2. Background:**

Amniotomy, i.e. artificial rupture of amniotic membranes, has become a common method used in management of both induction and augmentation of labor. It has been shown to shorten the duration of labor. Risks associated with amniotomy include ascending infection, fetal heart rate decelerations, umbilical cord prolapse, and rupture of vasa previa. While there are risks associated with amniotomy, there are also risks associated with prolonged labor, including an association with cesarean delivery and decreased fetal cord pH.

Timing of amniotomy in the management of induction of labor has not been widely studied. The limited studies have mixed results, but a recent meta-analysis suggests that early amniotomy shortens the length

of labor and has no effect on rates of cesarean section. However, these studies use a variety of methods for cervical ripening prior to amniotomy, which may affect the outcome as well. Additionally, the studies differed in whether they compared early amniotomy to delayed amniotomy or spontaneous rupture of membranes. Levy et al. showed longer labors with increased cesarean section rates in those receiving early amniotomy after cervical ripening with a Foley balloon. These results may be in part due to the fact that oxytocin infusion was not initiated in these subjects until the labor progress was deemed to be inadequate.

With the limited amount of published research, and conflicting results, more data is needed to be able to determine the ideal time for amniotomy during the management of the induction of labor, specifically when using a Foley balloon for cervical ripening.

The primary objectives of this study are to evaluate time to reach active phase of labor (defined as 6 cm or more of cervical dilation). The secondary objectives of this study are to evaluate in these subjects 1) cesarean section rates and indications, 2) occurrence of maternal complications including isolated maternal fever, chorioamnionitis, postpartum hemorrhage, endometritis, wound infection, and 3) occurrence of neonatal complications including umbilical cord prolapse, Apgar score <7 at 1 and 5 minutes, cord pH <7.0, NICU admission, neonatal infection. We will also be looking at time to vaginal delivery and vaginal deliveries within 24, 36 and 48 hours.

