#### **4.2. Randomization and Masking**

A confidential computer-generated simple randomization scheme (using STATA 16, Dallas, TX) has been prepared. A randomization log with group assignment, subject name, and medical record number will be used to track the randomization process.

Subjects will be randomized in a ratio of 1:1 for delayed or early amniotomy.

Due to the nature of the intervention, blinding of subjects or providers will not be possible.

The subject will be included in the analysis by intent-to-treat once the randomization assignment has been made.

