#### **4.4. Baseline Procedures**

Routine intrapartum care will be provided by the subject's managing obstetric team.

Trained and experienced research staff will be responsible for all research data abstraction.

The PI and collaborators will review and validate the diagnosis for all subjects identified to have the primary outcomes.

Maternal and neonatal outcomes will be assessed following delivery.

Subjects will be encouraged to call the principal investigator with any concerns.

Data collection forms will be used during these processes and charts will be reviewed up to 30 days postpartum. We will collect demographic data, as well as data related to the subject's intrapartum course, delivery, and immediate postpartum period while inpatient. Data on newborn status, including those admitted to the NICU, will be obtained from the infants' charts.

Subjects' participation will end after being discharged home from the hospital.

[figure not shown]

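### Endometritis is timed from an undefined operative procedure; on the plain reading, cases after spontaneous vaginal birth are not counted

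*Combined protocol and SAP*

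**What the plan says.** Section 4.10 states that endometritis must satisfy three conditions joined by AND. The first is the time window: "Infection occurs within 30 days after the operative procedure AND". The second is presumed involvement of the uterus. The third is at least one item from an evidence list. Two items are visible: purulent drainage from a drain placed through an abdominal or pelvic stab wound, and "Organisms isolated from an aseptically-obtained culture of fluid or tissue in the organ / space".

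The operative procedure is not defined anywhere in the document. Section 4.10 lists "Operative delivery rates" as an outcome separate from cesarean section, and it also counts vaginal deliveries within 24, 36 and 48 hours, so births without an operation are expected.

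Section 2 gives the secondary objective as "occurrence of maternal complications including isolated maternal fever, chorioamnionitis, postpartum hemorrhage, endometritis, wound infection", with no restriction by mode of delivery. It also names ascending infection among the risks of amniotomy, and Section 9.1 says complication rates may differ with earlier amniotomy.

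On ascertainment, Section 4.4 says "charts will be reviewed up to 30 days postpartum". The same section then describes postpartum data as gathered during the inpatient stay and ends participation at discharge. Section 4 ends participation at delivery.

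**The concern.** A woman who delivers vaginally without an operation has no date from which to count 30 days. On the plain reading she fails a mandatory condition and is recorded as free of endometritis even if a uterine culture is positive. The drain item supports that reading, since it belongs to a definition of surgical infection.

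The rule is also open to more than one interpretation. The 30 days coincide with the postpartum chart review, which suggests delivery as the anchor. The consenting text in Section 4.1 refers to Foley placement and amniotomy as procedures. Others may read cesarean only, or any operative delivery. In an unblinded trial, case status should not depend on which anchor the abstractor chooses.

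At stake is the completeness of a safety count that bears on a named risk of the intervention. A low count produced by the definition could be taken as reassurance.

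**Working it through.** **What the plan provides.** The documents give no endometritis rate and no cesarean rate, so there is no stated figure for this outcome to reproduce. The sample size rests only on the primary outcome: 2 × (1.960 + 1.282)² × 525² / 278² = 74.9, so 75 per group and 150 in total, as stated. The endometritis definition does not enter it.

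**Assumptions.** All rates below are assumed. Counted cases are those after cesarean, taken as the only operative procedure. True cases meet every condition except the anchor. Let c be the cesarean share and k the risk after cesarean divided by the risk after vaginal birth. Arms are 174 / 2 = 87 each.

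**1. Share of true cases missed** = (1 − c) / (c·k + 1 − c).

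| c | k = 1 | k = 5 | k = 10 |
|---|---|---|---|
| 0.15 | 0.850 | 0.531 | 0.362 |
| 0.30 | 0.700 | 0.318 | 0.189 |

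**2. Women missed**, at 1% to 3% risk after vaginal birth: 174 × 0.70 × 0.01 = 1.2, up to 174 × 0.85 × 0.03 = 4.4. Any operative vaginal births that are counted reduce this. The 1% to 3% must be the risk of infection that also meets the evidence list. For a woman without surgery, the only visible item she can meet is the culture, so the figures fall further if cultures are seldom taken. The extremes should not be combined freely: 3% with k = 10 would imply 30% after cesarean.

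**3. Would correcting the definition reveal an effect?** Take 20% cesarean in both arms, 5% risk after cesarean, and 2% (early) against 1% (delayed) after vaginal birth.
- True risk, early: 0.20 × 0.05 + 0.80 × 0.02 = 0.026.
- True risk, delayed: 0.20 × 0.05 + 0.80 × 0.01 = 0.018. The ratio is 1.44.
- Counted risk in each arm: 0.20 × 0.05 = 0.010. The ratio is 1.0.
- Expected true cases: 87 × 0.026 = 2.3 and 87 × 0.018 = 1.6.
- Chance that the corrected outcome is significant (two-sided 0.05, chi-square without continuity correction, exact enumeration): 5.0%.

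The corrected outcome would almost always miss this effect too.

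**4. Unequal cesarean rates.** With 30% against 20% and no effect within mode, the counted ratio is 0.30 / 0.20 = 1.5. The true ratio is (0.30k + 0.70) / (0.20k + 0.80): 1.0 at k = 1, 2.2 / 1.8 = 1.22 at k = 5, and 3.7 / 2.8 = 1.32 at k = 10. With equal cesarean rates and no effect, both ratios are 1.0. Section 1 points both ways on whether rates will differ: the cited meta-analysis found shorter induction "with no change in rates of cesarean section", while "one study showed longer labors with an increase in rates of cesarean section with early amniotomy".

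**5. Can that distortion produce a false finding?** At 15% to 30% cesarean and 3% to 10% risk after cesarean, counted cases per arm run from 87 × 0.15 × 0.03 = 0.4 to 87 × 0.30 × 0.10 = 2.6. At 30% against 20% cesarean, the chance of a significant result is 2.1% when the risk after cesarean is 5% (0.015 against 0.010) and 5.8% when it is 10% (0.030 against 0.020).

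**The case against.** **Other readings of the anchor.** If abstractors take delivery, amniotomy or Foley placement as the procedure, vaginal births count and nothing is lost. This is fair, and it is why the firm finding is that the anchor is undefined; exclusion of vaginal births follows only on the plain reading. It does not remove the need for a definition.

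**Scope.** Section 2 lists wound infection beside endometritis, and wound infection needs a wound, so being on the list does not prove that every mode of delivery must be able to yield a case. That weakens the argument from the list. But uterine infection does not need an operation, and the named risk of ascending infection does not depend on mode.

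**Intent to treat.** A reader might infer a breach of Section 4.2, "The subject will be included in the analysis by intent-to-treat once the randomization assignment has been made". The documents do not support this. The sentence governs who is analysed, and a woman with a vaginal birth stays in the denominator as a non-case.

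**A hidden effect or a false positive.** A reader might infer that the wording conceals an effect that a corrected definition would detect, or that it is likely to create a spurious significant difference. Steps 3 and 5 support neither: the chance of significance is 5.0% after correction, and 2.1% to 5.8% in the distortion scenarios.

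**Extraction.** The evidence list crosses a page break, so whether it once held more items cannot be judged here. The anchor line itself is intact.

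**Conclusion.** The point holds as a definitional gap in one secondary safety outcome. A mandatory condition refers to a procedure that the protocol does not define, and on its plain reading endometritis after spontaneous vaginal birth is not counted.

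The size is small in absolute terms: about 1.2 to 4.4 women of 174 on the assumed rates, and fewer if culture is rarely taken. As a proportion it may be large, 19% to 85% of true cases across the assumed range. The loss is to a descriptive count, not to a test with any useful power. The primary outcome and the sample size are unaffected.

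Confidence is high that the anchor is undefined. Every figure for the number of missed cases rests on assumed cesarean and infection rates.

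**What to change.** Before outcomes are abstracted:

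1. In Section 4.10, time endometritis from delivery, by any mode.
2. In the same edit, make sure the evidence list contains criteria that can be met after vaginal birth. Of the visible items, the drain presupposes surgery and only the culture remains, so changing the anchor alone would recover only culture-positive cases.
3. In Section 4.4, reconcile the 30-day postpartum chart review with the wording that limits postpartum data to the inpatient stay, so that the 30-day window is actually ascertained, and in the same way in both arms. Align the differing statements in Sections 4 and 4.4 on when participation ends.
4. Report endometritis counts by arm for all randomized women. Show counts by mode of delivery only as description, because mode arises after randomization and is itself an outcome.

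The cost is wording in the protocol and data form. No visits or subjects are added. If abstraction has begun, this one item must be rechecked for the vaginal births already done. If postpartum abstraction has in practice stopped at discharge, extending it to 30 days is additional chart work.

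### The endometritis definition in section 4.10 has no clinical route, so cases diagnosed and treated on clinical grounds alone are coded as absent and the outcome may be substantially under-counted

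*Combined protocol and SAP*

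**What the plan says.** Section 2 (Background) lists endometritis among the maternal complications to be evaluated as secondary objectives: "isolated maternal fever, chorioamnionitis, postpartum hemorrhage, endometritis, wound infection". Only section 4.10 (Secondary Outcomes) defines it. The definition opens with "Endometritis - must meet the following criteria" and has three limbs:

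- timing: "Infection occurs within 30 days after the operative procedure AND"
- site: "Infection presumed to involve the uterus AND"
- evidence: "Subject has at least one of the following", followed by two items, "Purulent drainage from a drain that is placed through a stab wound into the abdomen or pelvis" and "Organisms isolated from an aseptically-obtained culture of fluid or tissue in the organ / space".

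The list then moves on to postpartum hemorrhage.

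Two other infection outcomes in section 4.10 are given criteria, and both include a clinical route. Chorioamnionitis has a presumptive tier (fever plus at least one sign) and a separate confirmed tier based on laboratory findings. Neonatal infection accepts "positive cultures, or a suspicious clinical course that warranted treatment with antibiotics". Isolated maternal fever and wound infection are listed without criteria.

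On data sources, section 4.4 provides for routine care by the managing team and chart review to 30 days postpartum. Section 4.5 adds no postpartum visits, and section 8 names the electronic record as the source. No section schedules a uterine culture or any other test for endometritis.

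**The concern.** Both evidence items fit a post-surgical organ-space infection. They are available only if someone caring for the woman placed a drain or took an aseptic culture, and the protocol does not standardise either. Clinical suspicion of uterine infection is required but is not sufficient. Fever, uterine tenderness, abnormal lochia, a charted diagnosis and antibiotic treatment appear nowhere in the criteria. An abstractor who follows the definition has to code a clinically diagnosed and treated case as negative.

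Ascending infection is named as a risk of amniotomy in sections 2, 3 and 9.1, and section 9.1 allows that complication rates may differ with earlier amniotomy. If the definition misses many events, a very low count in both arms could be taken as reassurance about early amniotomy when it partly reflects how cases were counted.

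**Working it through.** **The plan's own figures.** No rate, power or sample size is stated for endometritis, so there is no figure on this outcome to reproduce. The number of women comes from section 13, which sizes the trial on time to 6 cm. With a difference of 278 min, SD 525, two-sided alpha 0.05 and power 90%, the two-sample normal formula gives 75 per group and 150 in total (power 0.9002), as stated. Allowing for 13% loss gives 150 / 0.87 = 172.4, or 173. The plan enrols 174, which is 87 per arm at 1:1.

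**The logic of the definition.** A case requires timing AND site AND (drain pus OR positive aseptic culture). Four situations follow:

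- Cesarean, clinical diagnosis, antibiotics, no drain, no culture: timing and site met, evidence not met. Not a case.
- The same woman with a positive aseptic culture of uterine fluid or tissue: all three limbs met. A case.
- The same woman with an aseptic culture that grew nothing: evidence not met. Not a case.
- Vaginal delivery without an operative procedure: the timing limb already fails as worded, whatever the evidence.

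The first and third rows show the gap. The fourth is a separate problem with the time origin; correcting it would leave the evidence limb as it is.

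**Illustration of size.** All rates and shares here are assumed. Expected counted cases = number of women × true rate × share with qualifying evidence.

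Per arm, at a true rate of 5%: 87 × 0.05 = 4.35 cases. With a share of 0% to 20%: 4.35 × 0 = 0 to 4.35 × 0.20 = 0.87 counted.

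Both arms together (174 women), with the chance of counting none = (1 − rate × share)^174:

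| True rate | True cases | Counted, share 10% | Chance of none | Counted, share 25% | Chance of none |
|---|---|---|---|---|---|
| 2% | 3.5 | 0.35 | 71% | 0.87 | 42% |
| 5% | 8.7 | 0.87 | 42% | 2.2 | 11% |
| 10% | 17.4 | 1.7 | 17% | 4.4 | 1% |

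Under-counting occurs whenever the share is below 100%. Its size depends entirely on the assumed share.

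**Effect on the comparison.** If the same share s qualifies in both arms and false positives are negligible, the observed risk ratio is (s × p1)/(s × p2) = p1/p2, which is unbiased. The risk difference shrinks to s × (p1 − p2), and events are lost. For assumed rates of 5% and 10%, full ascertainment gives 4.35 and 8.7 expected cases; with s = 20% these become 0.87 and 1.74.

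**The case against.** The best case for leaving the definition alone has four parts.

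- **Strictness is defensible in an open trial.** Providers know the allocation (section 4.2), and a clinical diagnosis could be made more readily in the early arm. This stands as a reason to keep the strict count, but not as a reason to omit a clinical tier, because the two can be reported side by side. The strict count is not immune either: the same unblinded providers decide whether to take a culture.
- **The comparison is weak under any definition.** With every case captured and assumed rates of 5% and 10%, the standard error is √[(0.05 × 0.95 + 0.10 × 0.90)/87] = 0.0398, so z = 0.05/0.0398 = 1.26. Then 1.26 − 1.96 = −0.70, and power is about 24%. This stands: a clinical tier recovers events but does not make the comparison decisive.
- **Other infection outcomes remain.** Isolated maternal fever, chorioamnionitis and wound infection are collected without a drain or culture requirement. They limit the loss but do not replace endometritis as a named outcome.
- **The list crosses a page break**, so a dropped item cannot be fully excluded. The text reads continuously, with no gap or redaction mark, and the sponsor can check this at once.

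A reader might go further and infer that clinically managed endometritis is never counted, that the total will be near zero whatever the truth, or that 80% to 100% of cases are missed. The documents support none of these. A clinically treated case with a positive aseptic culture does count if the other limbs are met. The protocol is silent on how often this unit takes cultures. The 80% to 100% figure is only the complement of an assumed 0% to 20%.

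**Conclusion.** The point holds as a matter of case definition. As written, endometritis supported by clinical evidence alone is coded as absent, after cesarean as well as otherwise, and the outcome may be substantially under-counted in both arms. The amount cannot be determined from the documents; the illustrative figures show the direction and the sensitivity to the assumptions, and are not estimates.

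The consequence is limited to one unpowered secondary safety outcome. Nor do the documents show a bias between arms: if qualifying evidence is equally likely in each, the risk ratio is preserved and the loss is one of information. What should be avoided is reading a low count in both arms as absence of a postpartum infection penalty. The change is worth making because the outcome relates to a named risk of the intervention and the edit is cheap.

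**What to change.** In section 4.10, add a pre-specified clinical tier to the evidence limb, on the pattern of the presumptive chorioamnionitis tier and the treated-clinical-course route for neonatal infection. One form would be a charted clinician diagnosis of endometritis treated with antibiotics, together with objective signs chosen by the investigators. The documents offer no source for particular signs or thresholds, so that choice is theirs. Keep the drain and culture items as a confirmed tier, and report clinical and confirmed cases separately by arm. If the investigators prefer the strict definition alone, they should give the reason and state that its count is not the incidence of endometritis.

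The cost is one added criterion and one line on the abstraction form; the charts are already reviewed to 30 days postpartum. The downside is that clinical diagnosis is made by unblinded providers, so the confirmed tier should always be shown alongside. If the time origin of the definition is also corrected, make both edits in a single rewrite.
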